**Randomization procedure:**

Patients will be identified by members of the treatment team in either the surgeon's clinic, pre-assessment clinic, or preoperative area. Patients who have opted out of research will not be asked to participate in the study. Patients will be approached to consent for the study by a surgeon, anesthesiologist, or member of the research team. Patients who agree to participate in the study will sign both a study consent and HIPAA authorization allowing the use of specified information contained in medical records for research purposes.

A random number generator will be used to determine if the patient will have pectoralis liposomal bupivacaine infiltration or bupivacaine infiltration directly into the incision space. The primary or co-investigator will access the number generator in the pre-op area. The website [www.random.org](http://www.random.org) will be used as the random number generator.

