## **Ultrasound-guided Pectoralis 1 and 2 block with liposomal bupivacaine for breast surgery: A prospective randomized study.**

**Design:** Level I randomized prospective outcomes study comparing two groups of patients. One group will receive liposomal bupivacaine for a pectoralis (“Pec”) block infiltration and the other will receive incisional bupivacaine infiltration by the surgeon.

**Sample Size:** 112 patients

**Study Duration:** Approximately 18 months

**Population:** Patients presenting to the University of Minnesota Medical Center, M health Ambulatory Surgery or Fairview Maple Grove Clinics Ambulatory Surgery Center, for elective lumpectomy and partial mastectomy procedures +/- axillary node dissection.

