For the surgeon infiltration, the patient will be brought directly to the operating room where intraoperative anesthetic with an opioid-sparing MAC technique will be provided as described below. Just prior to the skin incision, 0.25% bupivacaine will be used to infiltrate the dermis and subcutaneous space in the proposed incision. Throughout the procedure, additional incisional bupivacaine infiltration into the surrounding tissues will be performed as needed for local anesthesia. A total of up to 30 mL of 0.25% bupivacaine will be divided equally for the two sides of the incision. An additional 5 mL of 0.25% bupivacaine will be infiltrated into the pectoralis major muscle at the deep margin of resection. Accidental intravascular injection is minimized by continuous needle movement and frequent aspiration.

The following vital signs will be monitored throughout the procedure: Heart rate, blood pressure, oxygen saturation, and respirations, and patient's state of consciousness. We will monitor the patient until they are brought to the operating room for surgery.

All patients will receive multimodal analgesia in the preoperative area. They will receive 975 mg of oral acetaminophen and 300 mg of gabapentin orally prior to surgery. The intraoperative anesthetic will be an opioid-sparing MAC anesthetic. If patients are unable to tolerate procedure under MAC they would be converted to a general anesthetic with an laryngeal mask airway (LMA). For those patients receiving a lumpectomy with axillary dissection, they will receive a general anesthetic with LMA. Patients will receive IV midazolam 0-2 mg followed by 40-100mg of IV lidocaine, and followed by a propofol infusion and a 0.25 mg/kg bolus of ketamine followed by 0.25 mg/kg /hour infusion of ketamine. Opioids will be avoided unless HR or BP increases by 20 % above baseline. Then only short acting opioids (fentanyl) will be given.

In the recovery room if the patient experiences pain greater than 5/10 they will receive either IV or oral pain medications. If pain score is less than 5 patients will get non opioid medications unless the patient desires an opioid medication.

When the operation is complete the patient will either be brought to the PACU or Phase II. Each day a member of the research team will contact and evaluate the patient for signs of complications and ask the patient their minimum and maximum pain score

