  - Amount of opioids left over after 3 days
  - Presence of nausea/vomiting in 3 days post operatively
  - Occurrence of any subsequent re-admission over the ensuing 1 month and any complications

The collected data will be compared between groups on a regular basis in order to evaluate the safety and efficacy of the study. All data will be stored in secure locations in the Research Office. Research coordinators working with physicians to collect data at appropriate intervals will ensure complete follow-up. Research coordinators will periodically check physician schedules to ensure that patients being seen for follow-up complete all required questionnaires. Monthly meetings will also be conducted to ensure all patients needing to be evaluated are seen at the appropriate time intervals and that all data is being entered into the appropriate database.

**Data Safety Monitoring:** Authorized study staff and investigators who have gone through HIPAA, CITI, and other data security training through the University of Minnesota will be collecting, managing, and analyzing data. All serious adverse events will be brought forward to the Anesthesia Data Safety Monitoring Board that is comprised of various senior staff anesthesiologists. A formal determination concerning the severity of the risk and the recommended actions required will be submitted in writing to the principle investigator. This report will be submitted to the Institutional Review Board along with the required UPIRTSO documents.

**Statistical Considerations:** The primary outcome measurement used in this study is total opioid use

A sample size of 112 (56 per group) will be enrolled in order to power our study at 80% to detect a 35% decrease in total post-operative opioid usage for our treatment group versus the control with an  $\alpha=0.05$ . This sample size was estimated based on previous estimates for postoperative analgesic consumption from similar trials reported in the Tam (2015) meta-analysis paper.

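### Axillary dissection, which decides the type of anesthetic, is neither balanced at allocation nor named as a factor in the planned analysis

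*Combined protocol and SAP*

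**What the plan says.** The Randomization procedure section contains the entire allocation plan. "A random number generator will be used to determine if the patient will have pectoralis liposomal bupivacaine infiltration" or incisional infiltration, and "The primary or co-investigator will access the number generator in the pre-op area". The generator is a public website. No ratio, block size, prepared list, stratification factor or minimization is given there or elsewhere.

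The Statistical Considerations paragraph sets the target: "A sample size of 112 (56 per group) will be enrolled", to give 80% power to "detect a 35% decrease in total post-operative opioid usage for our treatment group versus the control". It gives no mechanism for reaching equal arms.

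The opening synopsis defines the population as patients presenting "for elective lumpectomy and partial mastectomy procedures +/- axillary node dissection". The Treatment technique section then separates them by anesthetic: "For those patients receiving a lumpectomy with axillary dissection, they will receive a general anesthetic with LMA". The others have an opioid-sparing MAC anesthetic and go to general anesthesia only if they cannot tolerate it.

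The Outcome Measurements section plans ANOVA for parametric data and chi-squared methods otherwise. It allows stratification of the data where appropriate and lists one variable, pre-operative pain modality, which it does not define. Axillary dissection is not named.

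**The concern.** Axillary dissection means more surgery and, under this protocol, a different anesthetic. Both plausibly raise opioid use, which is the primary outcome. The anesthetic type also bears on conversion to general anesthesia, a secondary objective. A trial can deal with such a factor by balancing it at allocation or by adjusting for it in a prespecified model. This plan does neither.

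With 112 patients, and perhaps only a couple of dozen axillary cases, chance alone can place noticeably more of them in one arm. An unadjusted comparison would then partly reflect the surgical mix. If the excess fell in the block arm it would hide part of a real effect; in the control arm it would exaggerate one. If adjustment is considered only after the imbalance is seen, the choice becomes open to dispute.

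**Working it through.** **1. The plan's own sample size.** No standard deviation or control mean is stated, only a reference to earlier trials, so 56 per group cannot be reproduced directly. Solving backwards with two-sided alpha 0.05 (sidedness is not stated) and 80% power:

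- standardized difference = (1.960 + 0.842) × √(2/56) = 0.529
- implied coefficient of variation = 0.35 / 0.529 = 0.66

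This value is used below where power is needed.

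**2. Arm sizes under a simple 1:1 draw.** With arm size distributed as Binomial(112, 0.5):

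| Outcome | Probability | Power at that split |
|---|---|---|
| exactly 56/56 | 7.5% | 80.0% |
| 51/61 or worse | 39.5% | 79.7% at 51/61 |
| 46/66 or worse | 7.2% | 78.7% at 46/66 |

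Averaged over all splits, power is 79.6%, a loss of about 0.4 percentage points. Equal arms are not guaranteed, but arm size is not where the harm lies.

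**3. Imbalance in axillary cases.** The documents give no expected share, so 10%, 20% and 30% are assumed. With m axillary patients, the number in one arm is X ~ Binomial(m, 0.5), and the gap between arms is |2X − m|.

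| Assumed share | m | P(gap of 6 or more) |
|---|---|---|
| 10% | 11 | 6.5% |
| 20% | 22 | 28.6% |
| 30% | 34 | 39.2% |

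At m = 22, a gap of 6 is a 14 v 8 split. A gap of 8 or more (15 v 7 or worse) has probability 13.4%. The mean gap is 3.7 patients.

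**4. What a 14 v 8 split does to the comparison.** Take 56 per arm and assume that axillary patients use a fraction r more opioid than the others, with r from 0.5 to 1.0.

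- Shift in units of the non-axillary mean: (14 − 8)/56 × r = 0.107 × r, which is 0.054 to 0.107.
- Overall mean in the same units: 1 + (22/112) × r, which is 1.098 to 1.196.
- Shift as a share of the overall mean: 0.054/1.098 = 4.9%, to 0.107/1.196 = 9.0%.
- Against the 35% target: 4.9/35 = 14%, to 9.0/35 = 26%.

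The division by the overall mean matters, because the 35% target is a share of average use and not of use among non-axillary patients. Treating the overall mean as the base of the 35% is a simplification.

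**5. Effect on the test, given such a split and no adjustment.** The planned effect sits 1.960 + 0.842 = 2.802 standard errors from zero.

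- Excess in the block arm: 2.802 × (35 − 4.9)/35 = 2.41, so power is about 67%. With the 9.0% shift it is 2.802 × 26.0/35 = 2.08, about 55%.
- No true effect: the chance of p < 0.05 given the split is about 7% (r = 0.5) to 11% (r = 1.0).

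These are conditional on that split. Over all possible draws the error rate stays at its nominal level.

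**6. Cost of adjusting.** At 14 v 8 the axillary proportions are 0.250 and 0.143, a difference of 0.107, and the overall proportion is 0.196. The squared correlation between arm and axillary status is 0.107² × 0.25 / (0.196 × 0.804) = 0.018. Variance inflation is 1/(1 − 0.018) = 1.019, or about 2%.

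**The case against.** The strongest reply is that simple randomization is a valid method. Chance imbalance in any covariate is already part of the variation that the standard error covers, so no bias has been shown. That is right, and it limits the point to precision and credibility: the trial is run once, and a visible imbalance in a factor that decides the anesthetic would weaken its result.

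A reader might infer that the draw contradicts the stated 56 per group, or leaves the trial underpowered. The documents do not support that. The figure is a target, and the power cost of unequal arms is negligible. A reader might also want site as a stratum, since three sites are named. Nothing in the documents suggests that opioid use differs by site, so that extension does not stand.

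Three further cautions hold. The axillary share and the excess opioid use are assumed. At a 20% share, 71% of trials would have a gap smaller than 6. The protocol never uses the word unrestricted, nor says that dissection is settled before the draw. The first is the natural reading of the text, and the second is made plausible by the planned anesthetic, but both are inferences.

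It can also be said that adjustment alone does nearly all the work. That is largely true, and it sets the order of the fix. The stratification sentence in Outcome Measurements does not already supply it: it concerns the analysis, is left to judgment, and does not name this factor.

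**Conclusion.** The concern holds as a design choice worth improving; it is not an error that invalidates the trial. A likely strong predictor of the primary outcome is neither balanced by the stated allocation nor adjusted for in the stated analysis. For assumed axillary shares of 10% to 30%, the chance of a gap of 6 or more such patients is 7% to 39%, and 29% at 20%. With an assumed 50-100% excess in opioid use, a 14 v 8 split moves the arm difference by about 5-9% of the overall mean, or 14-26% of the effect sought. The gap in the text is certain. The size of its consequence depends on those two assumptions, for which the documents give no figures.

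**What to change.** First, in Outcome Measurements, name planned axillary dissection (yes/no) as a prespecified factor in the primary opioid model. Record the plan before allocation and analyze by that planned status, so that the factor cannot be affected by treatment. The trial already collects type of surgery, so the cost is one pre-allocation field, one sentence, and about 2% variance inflation at a 14 v 8 split.

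In addition, replace the per-patient draw in Randomization procedure with a pre-generated, concealed 1:1 list in permuted blocks of varying size, stratified by planned axillary dissection only. With blocks of 4 and 6, for example, an incomplete block leaves a gap of at most 3 patients in each stratum. The axillary gap then cannot exceed 3, and the total arm-size gap cannot exceed 2 × 3 = 6. This needs a one-time list and a revised paragraph, but no extra patients and no change in treatment. The drawback is that unblinded investigators could guess some allocations near the end of a block. Varying the block size and concealing the list limit this. No site stratum is needed.

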## **Subjects:**

Demographics: All patients undergoing elective breast lumpectomy and partial mastectomy at the University of Minnesota Medical Center, M health Ambulatory Surgery Center or Fairview Maple Grove Clinics Ambulatory Surgery Center, with all Pec infiltration to be placed by the Primary Investigator and other staff anesthesiologists on the perioperative and interventional pain service and surgeon infiltration to be done by the co-investigators.

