**Exclusion criteria:**

- Patient on chronic anticoagulation
- Pregnant women
- Non-english speaking patients
- Any individuals who are unable to give informed consent
- Any individual with diminished capacity to give informed consent
- Allergy to local anesthetics
- Patients who remain intubated overnight after surgery or who are unable to provide information regarding their pain immediately postoperatively
- Daily use of opioid for more than three weeks
- Significant liver disease, defined as liver enzymes greater than 3x the upper limit of normal
- Lack of patient cooperation including those patients who refuse a MAC anesthetic
- Patient with pectoral muscle involvement of tumor
- Contraindication to regional anesthesia
  - Infection at injection site
  - Inability to guarantee sterile equipment or sterile conditions for the block
  - Patient refusal
  - Severe Coagulopathy or bleeding disorder

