### **Enrollment procedures:**

Patients will be recruited from the group of adult surgical patients at the University of Minnesota undergoing partial mastectomy procedures. Patients will be approached in either the surgeon's clinic or pre-assessment clinic by a research staff member to determine their interest in participation. Subjects interested in the study will be presented with consent and Health and Insurance Portability and Accountability Act (HIPAA) forms, with the REDCap e-consent process being preferentially used. The patient will review the forms with the surgeon, anesthesiologist or other study staff. Subjects will be reminded that participation is completely voluntary, and that they may stop participation at any time without question or penalty. The surgeon or anesthesiologist will answer any questions that the subjects may have about the study. If the patient decides to participate, they will be asked to sign the consent and HIPAA forms. One copy will be saved for study records, and the subject will be provided with a copy of the forms for their own records. If they need additional time to consider enrollment, they will be asked if we can reach out to them by phone the night before surgery or if we should revisit the study with them on the day of surgery. If the patient is unable to be consented prior to day of surgery, the research staff will approach them in the preoperative surgical area. These patients will have significant time to review the study with research staff as well as the physicians performing the procedure due to the fact they arrive several hours prior to their scheduled surgery. All subjects will have enough time to ask questions about the study and the potential risks involved regardless of which venue they are consented. Any patient that refuses to participate in the study at any time point will be placed on a secured list to avoid duplicate attempts to recruit them. All forms will be locked and stored in a file cabinet in the research department. Enrolling consecutive patients will help reduce selection bias. Any patient who does not complete all necessary paperwork and answer questions at the appropriate time intervals will be eliminated from the study. Patients lost to follow-up, or patients who decide not to participate in the study after initial enrollment, or patients who are eliminated from the study for any reason will have their study records shredded and will not be included in the final data-analysis.

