### **Subject Identification:**

Subject names will be collected as part of the informed consent process, and are thus considered private data. At the time of consent, subjects will be assigned an independent study identification (ID) number that will be used subsequently throughout the study. All data sheets will be identified only by an ID number. Data will be stored in a locked file cabinet in the research office at UMMC. Consent forms will also be stored in a separate locked file cabinet. Web based data will be accessible only by the primary investigator and research staff. It will be password protected and any information that is printed will be stored in a locked file cabinet in the research office at UMMC.

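### A treating investigator draws each allocation on a public website with no binding-draw rule or log, and the study records of patients who leave are shredded, so neither redraws nor exits by randomised arm can be reliably checked

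*Combined protocol and SAP*

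**What the plan says.** **The draw.** Under Randomization procedure, a random number decides between the Pec block and incisional infiltration, and "The primary or co-investigator will access the number generator in the pre-op area". The generator named is random.org. The section says nothing more about how the arm is assigned.

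**Who treats.** Subjects describes the study "with all Pec infiltration to be placed by the Primary Investigator and other staff anesthesiologists", and "surgeon infiltration to be done by the co-investigators". Both roles that may draw the arm therefore also deliver treatment.

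**Patients who leave.** Enrollment procedures eliminates anyone who does not finish the paperwork or answer the questions on time. The destruction rule covers patients lost to follow-up, those who change their mind after enrolling, and those "eliminated from the study for any reason will have their study records shredded and will not be included in the final data-analysis".

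**An exclusion known only afterwards.** Exclusion criteria includes "Patients who remain intubated overnight after surgery or who are unable to provide information regarding their pain immediately postoperatively".

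**What survives.**
- Subject Identification: "At the time of consent, subjects will be assigned an independent study identification (ID) number" and "Consent forms will also be stored in a separate locked file cabinet".
- Enrollment procedures: "Any patient that refuses to participate in the study at any time point will be placed on a secured list".
- Project Medications: study drugs are entered in the hospital chart.
- Notification: the investigators are told when a participant is eliminated.

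**The concern.** There are two linked gaps.

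The first is what can happen once a draw has been seen. The person who reads the result may be about to treat the patient, and a public generator can be run again at once. The protocol does not say that the first result binds, and it asks for no record of draws.

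The second is what can be reconstructed later. If randomised patients leave and their study records are destroyed, the report cannot reliably state how many left each arm or why.

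The stake is the comparison of opioid use itself. If allocation were selected after the draw, no analysis could repair it, and a reader would have no means of checking. Blinded outcome assessment (Assessments, Blinding Procedure) protects the recording of pain and opioid use, not allocation. Consecutive enrolment limits selection before the draw, not after it.

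**Working it through.** **1. Can a redraw be seen?** The protocol describes no prepared list, independent custodian, rule linking number to arm, binding first draw, draw log, or defined moment of randomisation. A redrawn patient stays in the trial under the second result, and every later record agrees with that result. Redraws are invisible because there is no log; shredding plays no part in this.

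**2. Would the arm totals reveal it?** Hardly. With 112 simple 1:1 draws, the central 95% range for one arm is 46 to 66 (exact binomial, p = 0.5). Suppose a share f of patients is redrawn once whenever the draw is unwanted, always toward the same arm. The probability of that arm is then 0.5 + 0.25f. At f = 20% this is 0.55, and the count falls outside 46-66 only 18% of the time.

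**3. Can exits be counted by arm?**

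| Surviving record | What it can show | Arm drawn? |
|---|---|---|
| Study ID, consent form | That a patient enrolled | Not described |
| Refusal list | That a patient declined | Not described |
| Elimination notice | That a patient left | Not described |
| Medication record in chart | Treatment received, if treated | Not described |

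The chart separates the treatments actually given, because under Treatment technique only the Pec arm receives liposomal bupivacaine. It cannot show the arm drawn for a patient who left between draw and treatment, or for one who received the other treatment.

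**4. How large could the effect be?** The plan gives no redraw or drop rate, so this is illustration only.

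*Reference figure.* Statistical Considerations gives 56 per group, 80% power and alpha 0.05, but no mean or SD, so the 112 cannot be reproduced. Solving backwards (two-sided, an assumption): (1.960 + 0.842) × √(2/56) = 0.529 SD by the normal approximation, and 0.534 SD by the t-test.

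*Assumed inputs.* There is no true effect. A fraction f = 5-10% of patients is recognised beforehand as likely to use s = 0.5-1 SD more opioid than the overall average. SD is 1 within each prognosis class. The two classes then differ by s/(1 − f), and bias = (high-use share in control − high-use share in Pec) × s/(1 − f).

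At f = 10%, s = 1, the class gap is 1/0.9 = 1.111:
- (a) One redraw when a high-use patient is drawn to Pec: control 0.075/(0.075 + 0.45) = 0.143; Pec 0.025/(0.025 + 0.45) = 0.053; bias 0.090 × 1.111 = 0.100 SD. Patients moved: 112 × 0.10 × 0.25 = 2.8.
- (b) Redraw until control: 0.10/(0.10 + 0.45) = 0.182; bias 0.182 × 1.111 = 0.202 SD. Moved: 112 × 0.10 × 0.5 = 5.6.
- (c) Dropped after a Pec draw: bias 0.10 × 1.111 = 0.111 SD. Dropped: 5.6.

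Simulation over all four combinations of f and s (100,000 trials each, two-sided t-test; Monte Carlo standard error of the rates about 0.001):

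| Behaviour | Patients moved or dropped | Bias (SD) | False-positive rate |
|---|---|---|---|
| (a) One redraw | 1.4-2.8 | 0.03-0.10 | 5.1-7.7% |
| (b) Redraw until control | 2.8-5.6 | 0.05-0.20 | 5.7-16.7% |
| (c) Drop after draw | 2.8-5.6 | 0.03-0.11 | 5.3-8.3% |

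**The case against.** The strongest reply is that the plan is silent on these safeguards rather than opposed to them. A fresh random number cannot be foreseen, so ordinary foreknowledge of the next allocation is absent. Sealed envelopes would in fact create a hidden sequence that a fresh draw does not have. Harm requires an investigator to discard a valid result or drop a patient after seeing it, and most of the illustrated effects are small. All of this stands. It limits the severity and makes a logged, binding random.org draw acceptable as a minimum. It does not close the gaps, because the written procedure would neither stop a redraw nor reveal one.

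Four stronger readings are tempting, and the documents do not support them:
- *Allocation was manipulated.* Nothing indicates this. That each patient is drawn individually, at the time, is itself the natural reading rather than an explicit statement.
- *Shredding hides redraws.* A redrawn patient is not eliminated, so no record is destroyed. Shredding affects the count of exits only.
- *A dropped patient leaves no trace.* The ID, consent form, refusal list, elimination notice and chart may show that someone left, and the chart shows what a treated patient received. The postoperative exclusion applies after treatment, so the chart would normally show the treatment given in those cases. What is not secured is the arm drawn.
- *Eligibility is decided during surgery.* One inclusion heading can be read that way, but Entry Criteria requires documented confirmation, and the two criteria listed there (procedure and age) are ordinarily known beforehand.

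**Conclusion.** The point holds as two linked gaps that should be fixed. As written, the plan neither prevents nor reveals a redraw by an investigator whose role also delivers treatment. Its destruction rule also means that exits by randomised arm cannot be reliably counted, least of all those between draw and treatment.

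The size of any bias is unknown. With the inputs assumed here, one redraw or selective dropping shifts the comparison by at most 0.11 SD, about a fifth of the 0.534 SD that the trial can detect (0.111/0.534 = 0.21). Only repeated redraws at the extreme setting reach 0.20 SD (0.203/0.534 = 0.38) and a false-positive rate of 16.7%. A reader might infer that the trial is invalid without this change. That goes too far: the mechanism needs a valid draw to be overridden, and the effect is small under most of these assumptions. The case for acting is that the weakness could not be checked afterwards and is cheap to remove.

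**What to change.** **Randomization procedure.** Have someone who does not treat patients prepare a computer-generated list; a simple list is enough. After eligibility is confirmed, release one time-stamped, binding allocation per consented study ID. Use REDCap's randomisation module if available, otherwise sequentially numbered opaque sealed envelopes. At minimum, if random.org is kept, state that the first draw is binding and keep a time-stamped log of every draw by ID.

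**Enrollment procedures.** Replace shredding with retention of ID, arm, time and reason for leaving for every randomised patient, and report these counts by arm.

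**Exclusion criteria.** State that events after allocation do not remove a randomised patient from the record. The inclusion criteria need no change.

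**Cost.** Setting up one list and keeping a minimal record. The protocol mentions REDCap only for e-consent, so availability of the randomisation module must be checked. The consent text was not available for review; if it promises destruction of records, it needs matching wording.
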